4.2 Endpoints

Primary endpoint:

Requirement of pain medication (if patient experiences a pain intensity of NRS \geq 3) during the first 2 and 24 hours after surgery.

For evaluation of primary endpoint post-operative pain levels need to be evaluated by NRS at 0 min (admission to PACU), 15 min, 30 min, 45 min, 60 min, 75 min, 90 min, 105 min, 2 hours and 24 hours.

Secondary endpoints:

Maximum post-operative pain levels (NRS) within 2- and 24-hours post-surgery.

Post-operative nausea and vomiting (PONV) at 2- and 24-hours post-surgery.

Requirement of antiemetic medication in presence of post-operative nausea and vomiting (PONV) during the first 2 and 24 hours after surgery.

Post-operative comfort at 2- and 24-hours post-surgery.

Post-operative anxiety at 2- and 24-hours post-surgery.

Post-operative mental orientation grade after extubation, at admission to PACU and at 2- and 24-hours post-surgery.

Anesthesia wakeup time (time from end of surgery until extubation).

5 Study Methods

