On basis of a 1:1 randomization ratio, we calculated that a planned sample of 368 patients would provide the trial with approximately 80% power to detect a difference in postoperative pain therapy on the basis of an effect size of 0.3 at a two-sided alpha level of 0.05. With 5 participating study centers, approximately 70-80 patients need to be included per center.

The sample size calculation is based on a previously published meta-analysis by Rosendahl et al.⁷ Sample size calculation for a power of 80% was done using G*Power software (University Dusseldorf, Dusseldorf, Germany, http://www.psychologie.hhu.de/arbeitsgruppen/allgemeine-psychologie-undarbeitspsychologie/gpower.html).

⁶ Apfel CC, Korttila K, Abdalla M, et al. A Factorial Trial of Six Interventions for the Prevention of Postoperative Nausea and Vomiting. N Engl J Med 2004; 350(24): 2441-51.

⁷ Rosendahl J, Koranyi S, Jacob D, Zech N, Hansen E. Efficacy of therapeutic suggestions under general anesthesia: A systematic review and meta-analysis of randomized controlled trials. BMC Anesthesiol 2016;16(1).

 Caseley-Rondi et al. 1994; d = 0.459
 Korunka et al. 1992; d = 0.405
 Rosenberg et al. 1992; d = 0.384
 Williams et al. 1994; d = 0.323
 Mastropietro et al. 1998; d = 0.315
 Furlong-Read et al. 1993, d = 0.256
 Nilsson et al. 1993; d = 0.244

7 General Considerations

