7.1 Timing of Analyses

The final analysis will be performed after participation of 400 patients in this study.

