9.3 Exploratory Efficacy Analyses

Further analysis of exploratory analyses will be performed in accordance with section 9.

10 Safety Analyses

All adverse events which are directly connected to study procedures will be documented and reported by appropriate statistical methods in accordance with section 9.

Due to the non-invasiveness of the study procedure, no severe adverse events are expected to occur.

11 Figures

The following figures will be considered for presentation in final publication(s):

- Post-operative pain levels (NRS) at 2- and 24-hours post-surgery.
- Post-operative pain levels (NRS) over course of time: pre-operative, at 0 min (at admission to PACU), 15 min, 30 min, 45 min, 60 min, 75 min, 90 min, 105 min, 2 hours and 24 hours.
- Usage of pain medication (opioids as morphine equivalents, non-opioids as percentage of maximum daily dose) at 2 and 24 hours after admission to PACU.
- Post-operative nausea and vomiting (PONV) at 2- and 24-hours postsurgery.
- Requirement/Dosage of antiemetic medication in presence of post-operative nausea and vomiting (PONV) during the first 2 and 24 hours after surgery.
- Post-operative comfort at 2- and 24-hours post-surgery.
- Post-operative orientation grade after extubation, and at 2- and 24- hours post-surgery.

Figure types will be chosen by the trial steering committee and statistician. Measures of central tendency will be presented as mean (normally distributed continuous variables) and median (not-normally distributed continuous variables). Error bars will be presented as SD for normally distributed continuous variables and as IQR for not-normally distributed continuous variables. Bootstrapping technique with resampling may be considered for presentation of non-parametric values with mean and 95% confidence interval, where applicable.

12 Reporting Conventions

P-values ≥0.001 will be reported to 3 decimal places; p-values less than 0.001 will be reported as '<0.001'. The mean, standard deviation, and any other statistics other than quantiles, will be reported to one decimal place greater than the original data. Quantiles, such as median, or minimum and maximum will use the same number of decimal places as the original data. Estimated parameters,

not on the same scale as raw observations (e.g. regression coefficients) will be reported to 3 significant figures.

13 Technical Details

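### The 80% power in Section 6 fits one comparison of one continuous outcome, but the SAP never fixes the primary endpoint's scale, time point or test, and the figure does not carry over to a yes/no requirement

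*SAP*

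**What the plan says.** Section 6 states that 368 patients would give "approximately 80% power to detect a difference in postoperative pain therapy on the basis of an effect size of 0.3", at a two-sided alpha of 0.05 with 1:1 allocation. It names G*Power but neither the test nor the scale of the outcome. The supporting effects, taken from studies in a published meta-analysis, are all listed as d, from 0.244 to 0.459. No proportion or expected rate appears.

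Section 4.2 gives the primary endpoint as "Requirement of pain medication (if patient experiences a pain intensity of NRS" at or above 3), during the first 2 and 24 hours. Section 9.1 shortens this to post-operative pain medication at the same two times and refers to Section 9. That section offers a t-test, a Mann-Whitney test or a chi-squared test, according to the type and distribution of the variable.

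Section 5.4 (item 8) records post-operative analgesics as dose sums: opioids in morphine equivalents and, separately, non-opioids as a percentage of the maximum daily dose. Section 11 plots "Usage of pain medication (opioids as morphine equivalents, non-opioids as percentage of maximum daily dose") at 2 and 24 hours.

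On numbers of patients, Section 6 adds that "approximately 70-80 patients need to be included per center" across 5 centers, and Section 7.1 says "The final analysis will be performed after participation of 400 patients in this study".

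**The concern.** A power statement belongs to one variable, one time point and one test. Here at least three variables can claim to be primary: yes/no requirement, opioid dose and non-opioid percentage. Each has two time points, which makes six candidate comparisons. Section 9 then assigns the test from the variable's type and distribution, so the test is open as well.

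Two things are at stake. First, the comparison that decides success could be selected once the results are known, which a SAP exists to prevent. Second, if the comparison turns out to be yes/no, a null result would be read against an 80% claim that was not derived for it.

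**Working it through.** **1. Reproducing 368.** Inputs from Section 6: effect size 0.3, two-sided alpha 0.05, 1:1 allocation, power 80%.

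- Mann-Whitney, normal parent: the per-arm n is scaled by the asymptotic relative efficiency 3/π = 0.955. For n = 184, n' = 184 × 0.955 = 175.7. The noncentrality is 0.3 × √(175.7/2) = 2.81, and the noncentral t gives power 80.1%. With 183 per arm it is 79.9%. The smallest total is therefore 368, which is the stated figure. A simulation of 4,000 trials gave 80.8%.
- t-test: 80% is reached at 176 per arm, or 352 in total. With 368 it gives 81.9%.
- Normal approximation: 175 per arm, or 350 in total. Adding 5% gives 350 × 1.05 = 367.5, which also rounds to 368, but Section 6 mentions no such allowance.

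The rank test is thus an inference from the number. Each of these routes treats 0.3 as a standardised mean difference on a continuous outcome.

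**2. Power if the endpoint is yes/no.** The SAP gives no control rate, so the rate p0 is assumed and varied. The value 0.3 is turned into an intervention rate p1 in two ways:

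- latent-normal shift: p1 = Φ(Φ⁻¹(p0) − 0.3)
- logistic conversion: ln OR = −0.3 × π/√3 = −0.544, so OR = 0.580

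Power for two proportions is Φ{(|p0 − p1| − 1.96·SE0)/SE1}, with SE0 the pooled and SE1 the unpooled standard error. Example with p0 = 0.50, latent-normal, 184 per arm: p1 = 0.382, SE0 = 0.0518, SE1 = 0.0514, and (0.1179 − 0.1014)/0.0514 = 0.32, so power is 62.6%.

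| Assumed control rate | Latent-normal p1 | N = 368 | N = 400 | Logistic p1 | N = 368 | N = 400 |
|---|---|---|---|---|---|---|
| 30% | 20.5% | 56% | 59% | 19.9% | 61% | 65% |
| 40% | 29.0% | 60% | 64% | 27.9% | 69% | 73% |
| 50% | 38.2% | 63% | 66% | 36.7% | 73% | 77% |
| 60% | 48.1% | 63% | 66% | 46.5% | 74% | 77% |
| 70% | 58.9% | 61% | 64% | 57.5% | 70% | 74% |
| 80% | 70.6% | 55% | 59% | 69.9% | 61% | 65% |
| 90% | 83.7% | 43% | 46% | 83.9% | 41% | 44% |

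For 80% power at control rates of 50-80%, the total would be 552-658 (latent-normal) or 430-576 (logistic).

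**3. Power if the endpoint is a continuous dose.** One Mann-Whitney test at d = 0.3, normal parent, by number analysed: 350 gives 78%, 368 gives 80%, 380 gives 81% and 400 gives 83%.

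**The case against.** The strongest reply is that dose is what the SAP means. Item 8 of Section 5.4 defines post-operative analgesics only as dose sums, Section 11 plots them only as amounts, and the effects in Section 6 are d values. Where the SAP wants a binary item it says so, as with PONV in Section 5.4. On that reading the 80% is correct for a single comparison, and no figure in Section 6 is wrong. This stands as far as it goes, and it is why the endpoint should be called ambiguous, not binary. It does not settle the matter. Section 4.2 ties the requirement to a pain threshold, the antiemetic item in Section 11 names requirement and dosage side by side, and even the dose reading leaves two drug classes and two time points open.

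A second reply is that 0.3 might be Cohen's h for proportions, which would give about 82% with 368. The listed d values speak against it, and h = 0.3 would need 350 patients, not 368.

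A reader might also infer that 368, 350-400 and 400 contradict each other. They need not. 5 × 70 = 350 and 5 × 80 = 400 bracket both other figures. The analysis is per protocol and omits missing data (Sections 7.2, 7.4 and 8.1), so 400 recruited against 368 needed is a plausible margin of 32/400 = 8%. The SAP does not say so, but that is an omission and not a conflict.

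**Conclusion.** The concern holds as a failure to fix the primary variable, time point and test, together with a power statement that suits only the continuous reading. The arithmetic behind 368 is sound.

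A reader might go further and conclude that the trial has only 55-63% power. The SAP does not support that as a figure for this trial: it requires the yes/no reading, a control rate of about 30-80% and a latent-normal conversion, none of which the document states. The logistic conversion gives 61-74% over the same rates, and at a 90% rate the two give 43% and 41%. What is robust is the direction: under both conversions, at every rate tabulated, power stays below 80% with 368 and with 400 patients.

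On the dose reading, about 80% holds for one comparison with 368 analysed. The 83% for 400 holds only if nobody is excluded. Both rest on a normal-parent formula.

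**What to change.** In Sections 4.2 and 9.1, name one primary variable, one time point (or a multiplicity rule covering 2 and 24 hours) and one pre-specified test. The reading that fits Section 6 is cumulative post-operative dose, with the dose scale stated. It would be tested by Mann-Whitney regardless of any normality check and reported with a Hodges-Lehmann difference and 95% CI. The other scales and the other time point become secondary.

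In Section 6, name the test and the outcome scale. State that about 80% applies to that single comparison with 368 patients analysed, and about 83% only if all 400 are analysed. If 400 includes a margin for exclusions, say so.

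If yes/no requirement is to stay primary, replace the 80% with a power calculated for an explicit assumed control rate.

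The cost is wording, and no extra patients if dose is chosen. If yes/no is chosen, the sponsor must either accept a less favourable power figure or recruit more: roughly 430-658 in total for 80% under the conversions above, at control rates of 50-80%.

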7.1 Timing of Analyses

The final analysis will be performed after participation of 400 patients in this study.

7.2 Analysis Populations

Analysis will be performed 'per protocol'. All subjects who did not substantially deviate from the protocol as to be determined on a per-subject basis at the trial steering committee immediately before data base lock, will be included in the final analysis.

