5.3 Randomization and Blinding

Patients are assigned in a 1:1 ratio to intervention or control group by simple randomization technique (drawing lots), for each study center.

This is a double-blinded trial. Assignment to treatment group and conduct of study procedure is performed by independent study personnel, which is not involved in conduct of general anesthesia or post-operative treatment of pain. Medical personnel which is involved in treatment of the patient has no information about group allocation. Headphones of the audio player for therapeutically communication are placed on the ears of patients in control group as well (whereas no audio file will be played).

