7.4 Missing Data

Missing data will be excluded from each specific statistical analysis and reported.

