8.1 Protocol Deviations

Major deviations are defined as follows:

- Deviation from main study procedure (audio suggestion) like discontinuation during surgery of more than 10 minutes, wrong treatment in contrast to randomization.
- Violation of inclusion and exclusion criteria.
- Missing informed consent.
- Malfunction of the audio player.
- Unexpected transfer to ICU.

Patients with major deviations will be excluded in the 'per protocol' analysis (see section 7.2).

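### Per-protocol is the only analysis set, and it drops patients for events after randomisation, so the efficacy comparison is not the randomised one

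*SAP*

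**What the plan says.** Section 7.2 fixes the population for the final analysis: "Analysis will be performed 'per protocol". Patients who deviated substantially are left out, "as to be determined on a per-subject basis at the trial steering committee immediately before data base lock". No intention-to-treat or other as-randomised set is named. Sections 9.1 to 9.3 send the primary, secondary and exploratory analyses to section 9, which adds no further population.

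Section 8.1 lists the major deviations that lead to exclusion. Four of the grounds are events after randomisation:

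- departure from the audio procedure, "like discontinuation during surgery of more than 10 minutes, wrong treatment in contrast to randomization" (two grounds in one bullet);
- "Malfunction of the audio player";
- "Unexpected transfer to ICU".

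Eligibility violations and missing consent are also on the list.

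On what controls receive, the SAP says two things. Section 5.3 has them wear headphones, "whereas no audio file will be played". The schedule in 5.1 has a row for a placebo version of the audio suggestion during surgery.

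**The concern.** Randomisation makes the arms comparable as they were allocated. Once patients are removed because of what happened afterwards, a difference between those who remain can reflect who was removed as well as what the intervention did. Where the aim is to show a difference, the as-randomised comparison guards against this, and here it is not planned at all. Excluded patients would appear in no efficacy analysis, so a reader could not see whether the result depends on leaving them out.

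The make-up of the list adds to the problem. Audio that is not playing cannot be interrupted, and a fault in a silent player is unlikely to be noticed. On the wording of 5.3, those two grounds would remove mainly intervention patients.

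**Working it through.** **1. The plan's own figure.** Section 6 gives 368 patients for about 80% power at an effect size of 0.3, two-sided alpha 0.05, 1:1. A two-sample t-test needs 176 per arm (352). A Mann-Whitney test with asymptotic relative efficiency 3/π under normality needs 184 per arm, which is 368, with power 0.801. The stated figure is reproduced. Section 7.1 sets the final analysis at 400 patients, so 200 per arm is used below.

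**2. Which exclusions can occur in which arm.**

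| Ground in 8.1 | Arises after randomisation? | Arm |
|---|---|---|
| Audio stopped for more than 10 minutes | yes | mainly intervention, if 5.3 holds |
| Player malfunction | yes | mainly intervention, if 5.3 holds |
| Wrong treatment | yes | either |
| Unexpected ICU transfer | yes | either |
| Eligibility violation | partly: surgery length and need for intensive care (5.2) become known only during or after surgery | either |
| Missing consent | no | either |

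If the placebo audio in 5.1 is a track that is actually played, the first two rows could occur in controls as well, and the imbalance would weaken.

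**3. Illustration of size.** The SAP gives neither the share excluded nor how excluded patients differ. Both are assumptions here, as is a continuous outcome on an SD scale. Assume no true effect and exclusions in the intervention arm only.

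Let q be the share excluded and s the amount, in SD, by which the excluded are worse than the average of their whole arm. Those retained are then better than that average by

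shift = q·s / (1 − q).

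If the gap g is measured against the retained patients instead, shift = q·g. The two agree because g = s / (1 − q).

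Standard error = √(1/n₁ + 1/200), with n₁ = 200(1 − q). With λ = shift / SE, the two-sided rejection probability is Φ(λ − 1.96) + Φ(−λ − 1.96).

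- q = 2.5%, g = 0.25: shift 0.025 × 0.25 = 0.006; n₁ = 195; SE 0.1006; λ = 0.06; error about 5.0%.
- q = 5%, s = 0.5: shift 0.025 / 0.95 = 0.026; n₁ = 190; SE 0.1013; λ = 0.26; error 5.8%.
- q = 5%, s = 1: shift 0.05 / 0.95 = 0.053, which is 18% of the planned 0.3; λ = 0.52; error 8.1%.
- q = 8%, s = 0.5: shift 0.04 / 0.92 = 0.043; n₁ = 184; SE 0.1022; λ = 0.43; error 7.1%.
- q = 8%, s = 1: shift 0.08 / 0.92 = 0.087, which is 29% of 0.3; λ = 0.85; error 13.6%.

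The calculation is symmetric: if the excluded were better than average by the same amounts, the shift would run against the intervention.

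**4. Power.** With 200 per arm, t-test power at 0.3 is 0.849. With 190 against 200 it is 0.840, and with 180 against 200 it is 0.830. Lost numbers matter little; the issue is selection.

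**The case against.** Several stronger readings are tempting, and the SAP does not support them.

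*That the audio exclusions can occur only in the intervention arm.* Wrong treatment stands in the same bullet and can occur in either arm. The placebo entry in 5.1 conflicts with 5.3. The one-arm argument covers interruption and malfunction only, and only if 5.3 is the correct description.

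*That the bias favours the intervention.* Nothing in the SAP says that patients with interrupted audio have more pain. A purely technical failure unrelated to prognosis gives no bias when there is no true effect. Long or complicated surgery might link the two, but the SAP does not show this.

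*That the type I error is inflated.* That is conditional. A gap of 1 SD is more than three times the planned effect, and the low end of the range shows practically no inflation. The SD scale also assumes a continuous endpoint, whereas 4.2 words the primary endpoint as a requirement for medication, which may be binary.

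*That the steering committee decides with knowledge of arm.* The SAP is silent. It calls the trial double-blinded, places the decision before database lock and lists the major deviations. Masking of the committee may be described in the protocol, which is not shown.

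These objections limit what can be said about direction and size. They leave the main point standing: even if exclusions were balanced between arms, the only planned comparison would still be among patients selected after randomisation.

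**Conclusion.** The point holds as a defect in the choice of analysis set. Section 7.2 makes per-protocol the sole population, 8.1 removes patients for post-randomisation events, and no other section supplies an as-randomised analysis. All efficacy results depend on it.

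The size cannot be determined from the SAP. Under the assumptions shown, the type I error ranges from essentially nominal to 13.6%. Those figures illustrate what is possible and do not estimate what will happen. The imbalance between arms is conditional on 5.3 being right about the control condition.

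**What to change.** - **7.2:** make the primary analysis all randomised, consented and operated patients with outcome data, each in the arm to which they were randomised, whatever happened to the audio. Include patients transferred to ICU where their outcomes are available.
- **7.2 and 8.1:** keep per-protocol as a supportive analysis. Close the list in 8.1, whose first bullet now gives examples only. Have exclusions decided without access to outcome data and, as far as possible, without knowledge of arm. Masking to arm will be imperfect, because a recorded interruption itself suggests the intervention.
- **5.1 and 5.3:** reconcile the description of what controls receive.

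The cost is SAP wording, one extra analysis set and some dilution by non-adherent patients. If 5% or 8% of the intervention arm gained nothing, an effect of 0.3 would become 0.3 × 0.95 = 0.285 or 0.3 × 0.92 = 0.276. With 200 per arm (SE √(2/200) = 0.1), approximate power is Φ(2.85 − 1.96) = 81% or Φ(2.76 − 1.96) = 79%, close to the planned 80%.

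### Section 7.2 lets the steering committee decide case by case, after outcomes are recorded, who leaves the only analysis set, without stating that the review is blind or bound by the 8.1 list

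*SAP*

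**What the plan says.** Section 7.2 (Analysis Populations) plans a single analysis set: "Analysis will be performed 'per protocol". It keeps "All subjects who did not substantially deviate from the protocol", and this is "as to be determined on a per-subject basis at the trial steering committee immediately before data base lock". The section does not define substantial deviation. The SAP names no as-randomised set.

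Section 8.1 (Protocol Deviations) uses a different term. It opens with "Major deviations are defined as follows" and gives five bullets: deviation from the audio procedure, violation of the eligibility criteria, missing consent, malfunction of the audio player, and unexpected transfer to ICU. The first bullet introduces its examples with the word *like*, and one of them is "wrong treatment in contrast to randomization". The consequence is stated as automatic, with a pointer back: "Patients with major deviations will be excluded in the 'per protocol' analysis (see section 7.2").

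Section 5.3 (Randomization and Blinding) calls the trial double-blinded. It gives assignment and the study procedure to independent personnel and adds: "Medical personnel which is involved in treatment of the patient has no information about group allocation". The steering committee is not mentioned. Control patients wear the headphones, "whereas no audio file will be played".

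**The concern.** Three features of the exclusion decision come together.

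- **Discretion.** The criterion in 7.2 is an undefined judgement made one subject at a time, and nothing says that the 8.1 list is its full content.
- **Timing.** The last outcome is at 24 hours, so a meeting immediately before lock takes place when every endpoint is already on file.
- **Knowledge.** The SAP does not say that the committee works without sight of arm or outcome.

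If the people deciding know a patient's arm and analgesic use, the decision to keep or drop that patient can be influenced by the result, without any intent. Neither the p-value nor the confidence interval allows for this. With no as-randomised analysis planned, a reader of the report could not see what the exclusions did to the estimate. The set in question carries every efficacy result.

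**Working it through.** **Step 1. Is the committee bound by the 8.1 list?**

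| Question | Section 7.2 | Section 8.1 |
|---|---|---|
| Criterion | substantial deviation, undefined | major deviation, five bullets |
| How applied | committee, subject by subject | automatic exclusion |
| Closed? | no | no: first bullet gives examples only |
| Link | none to 8.1 | refers to 7.2 |

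The pointer from 8.1 to 7.2 permits the reading that the committee merely applies the list. The different terms and the subject-by-subject wording permit the reading that it may go beyond the list. The text does not settle which. Even on the first reading, the open first bullet leaves something to judge.

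**Step 2. What could the committee know?** Section 5.3 speaks only of those treating the patient. Treatment that differs from the randomised one cannot be recognised without the allocation. An interruption of the audio points to the intervention arm, because controls have no file playing; a player malfunction tends to do the same. The only listing order given in the SAP (section 8) is by site, treatment and subject. The SAP does not say that those listings go to the committee, but it describes no masked listing either.

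**Step 3. The plan's own figure.** Section 6 gives 368 patients for an effect size of 0.3, two-sided alpha 0.05, about 80% power and 1:1 allocation. A two-sided t-test needs 175.4 per arm, so 176 and 352 in total. Dividing by the Mann-Whitney asymptotic relative efficiency of 0.955 gives 2 × 175.4/0.955 = 367.3, so 184 per arm and 368 in total. The figure is reproduced. Section 7.1 analyses after 400 patients, which leaves 400 − 368 = 32 (8%) that could be excluded before the set falls below the planned size.

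**Step 4. Size of a selective exclusion (illustration).** The documents do not say how many exclusions to expect. Assume a continuous outcome with SD 1, and k patients removed from one arm of n whose values average 2 SD above that arm's mean. The arm mean then falls by 2k/(n − k).

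| n per arm | k | Shift (SD) | Share of 0.3 |
|---|---|---|---|
| 184 | 5 | 10/179 = 0.056 | 19% |
| 184 | 10 | 20/174 = 0.115 | 38% |
| 200 | 5 | 10/195 = 0.051 | 17% |
| 200 | 10 | 20/190 = 0.105 | 35% |

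**Step 5. Effect on the type I error (illustration).** Simulation with no true effect, normal outcome, 200 per arm, two-sided t-test at 0.05, 20,000 runs, with exclusions from the intervention arm only:

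| Excluded | Worst k removed | Random k from the worse half |
|---|---|---|
| 0 | 0.052 | 0.051 |
| 2 | 0.062 | 0.051 |
| 4 | 0.083 | 0.054 |
| 8 (2% of 400) | 0.161 | 0.058 |
| 16 (4% of 400) | 0.385 | 0.100 |

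Fully outcome-driven removal does serious damage at small numbers. Weak selection does little until the numbers grow.

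**The case against.** **The committee may well be blind.** The SAP calls the trial double-blinded without limiting the statement, and the committee's access to data may be laid down in a protocol or charter that is not at hand. This stands. A reader might infer from 5.3 that the committee is unblinded; the document does not say so. What can be said is that blinding of this review is not stated where the review is defined.

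**There may be only one rule.** With the pointer in 8.1 to 7.2, a natural reading is that 8.1 gives the criteria and 7.2 says who applies them and when. A reader might infer that the two sections contradict each other, so that a patient with a listed deviation could be kept. That does not fit the mandatory exclusion in 8.1. What remains is that two terms are used for one concept and that the list is neither closed nor declared binding on the committee.

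**The decision precedes lock.** That fixes the set before the final analysis and is a partial safeguard. It protects against selection on results only if the review is also blind.

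**The figures are chosen extremes.** This also stands. Nothing in the SAP suggests that exclusions would all come from one arm and from its upper tail. Under milder selection, eight exclusions leave the type I error near 6%.

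**The harm depends on per protocol being the only set.** Largely true: if an as-randomised analysis became primary, these exclusions would no longer touch the primary result. They would still decide the per-protocol result, and as the SAP stands they decide everything.

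**Conclusion.** The point holds as a weakness in how the exclusion rule is fixed. It does not show that bias has occurred or that the committee is unblinded. Section 7.2 gives a per-subject judgement of an undefined criterion to a committee at a time when outcomes exist, and the SAP does not state that the judgement is blind to arm and outcome or limited to the 8.1 list. That list has an open first item, and some of its items need or tend to reveal the allocation. Exclusions could therefore depend on results.

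The size is unknown. The worst-case illustration of 0.056 SD (19% of the planned 0.3) for five removals from one arm of 184 rests on three assumptions: a continuous outcome, removals from one arm only, and an average 2 SD above its mean. Exclusions unrelated to outcome would cause no such shift on average. The change is worth making before lock because it is cheap and the set concerned carries every efficacy result.

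**What to change.** 1. **Section 7.2:** replace the per-subject judgement of substantial deviation with a reference to patients who have a major deviation as defined in section 8.1.
2. **Section 8.1:** remove the open-ended wording from the first item, so that it names only interruption of the audio for more than 10 minutes and treatment other than that randomised. State that the list is exhaustive and that an unlisted deviation does not lead to exclusion.
3. **Blind application:** state that the committee applies the list from a listing that shows neither arm nor any outcome value (NRS, analgesic or antiemetic use, PONV, comfort, anxiety, orientation, wakeup time). For the audio and wrong-treatment items, the independent study personnel described in 5.3 supply only a yes/no flag.
4. **Sign-off:** the exclusion list is signed before database lock and before any member sees outcome data by arm.
5. **Reporting:** give the number of exclusions by arm and reason.

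The cost is SAP wording and one masked listing; no study procedure changes. The downside is that the committee can no longer judge unusual cases on their merits, so the list must be checked for completeness before it is closed.
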